5.1.1 Study Date Range and Duration

The duration of this study is 12 weeks.

5.1.2 Number of Study Sites

This is a dual site study that will be carried out at Yale and Medical University of South Carolina. The study will use remote/telehealth procedures, as much as possible, as detailed below

5.2 Outcome Variables

5.2.1 Primary Outcome Variables

The primary outcome will be abstinence from vaping at week 8. Abstinence is defined as no vaping, not even a puff, every day for the last 7 days via self-report (i.e., 7 day point prevalent abstinence).

5.2.2 Secondary Outcome Variables (if applicable)

5.2.3 The secondary outcome will be abstinence from vaping at week 12. Abstinence is defined as no vaping, not even a puff, every day for the last 7 days via self-report (i.e., 7 day point prevalent abstinence).

5.2.4 Exploratory Outcome Variables (if applicable)

N/a

5.3 Study Population

Participants: This study will use various media outlets to recruit adults who report current e-cigarette use in South Carolina (for MUSC) and in Connecticut (for Yale). Advertising will target e-cigarette users who have a desire to quit and are willing to undergo treatment, set a quit date, and attempt to maintain e-cigarette abstinence. Mono-vapers will click the link in our Craigslist and social media ads which will open a screening survey through REDCap on their mobile devices. If the individual meets pre-screening eligibility, the research staff will call the participant to schedule an intake to confirm final eligibility for the study.

5.3.1 Number of Participants

We plan to enroll 40 participants across two sites. As with previous studies, we will make every effort to maximize participant retention via a thorough informed consent process, careful screening, and other practices.

5.3.2 Eligibility Criteria/Vulnerable Populations

Prospective participants will be screened on initial eligibility criteria.

Following completion of the screener, research staff will inform potential patients of their initial eligibility status. Those who meet initial criteria will be invited to attend an intake (via HIPPA compliant telehealth platform since this study is fully remote) to provide written informed consent and complete final screening for inclusion/exclusion criteria. Eligible individuals will be randomized to their condition to begin immediately after intake.

Inclusion criteria:

1. age 18+;
2. daily use of an e-cigarette containing nicotine (defined as use for at least 25 days out of the past month);
3. use of an e-cigarette containing nicotine > 6 months;
4. have desire to quit e-cigarettes, are willing to set a quit date and maintain e-cigarette abstinence;
5. have daily access to a smartphone or have regular (daily) access/use of email; and

6. and live in South Carolina or Connecticut.
7. No use of combustible tobacco in the past 30 days (including cigarettes, cigarillos, etc.).
 - a. In the 2 months prior to the past 30 days, patients must not use combustible tobacco for >1 time per week.
8. No use of non-combustible nicotine products (ie pouches, smokeless tobacco, etc.) in the past 30 days.
 - a. In the 2 months prior to the past 30 days, patients must not use non-combustible nicotine products (ie pouches, smokeless tobacco, etc.) for >1 time per week.

Exclusion criteria:

1. Vulnerable Populations: We will not be enrolling vulnerable populations, specifically pregnant women, children, prisoners, or institutionalized individuals.
2. We also will not enroll participants incapable of providing their own consent. The rationale will be provided to the individual as well as his or her family members. Referrals for further evaluation, including urgent or emergent evaluation, will be made as needed and clinically warranted.
3. We will exclude individuals with medical contraindications for varenicline use (i.e., severe renal impairment)
4. We will exclude anyone currently using smoking cessation medications.
5. Individuals will also be excluded if another household member is currently enrolled in the study.
6. Individuals will be excluded if not proficient in English.
7. Verification of Non-Pregnancy: Females ages ≤ 55 will be mailed a commercially available pregnancy test to verify non-pregnancy. Written confirmation of negative pregnancy test via REDCap will be required prior to enrollment in the trial. Participants are also informed that they should let us know if they become pregnant during the trial. Medications will not be sent until this verification is in place. These procedures are based on the MUSC IRB approved STARS protocol (MUSC IRB Pro00098479).

6 Methods

6.1 Treatment

6.1.1 Identity of Investigational Product

Varenicline tartrate (sometimes called Chantix, Apo-Varenicline, or Par-Varenicline), is a prescription medication for smoking cessation. The oral supply we will use is approved by the US Food and Drug Administration (FDA), Par-varenicline. Many studies show that varenicline can help people who smoke quit smoking. Varenicline is a prescription medication, which usually means that you must see your doctor to get it. Varenicline is used to treat tobacco use dependence. It helps reduce cravings for tobacco use and decreases the pleasurable effects of cigarettes and other tobacco products.

6.1.2 We will be receiving the medication from the YNNH Investigational Drug Service. They will be the ones storing the medication. They will also do the encapsulation of the active drug and placebo. Written instructions will be attached to the medication from the pharmacy and the research staff will distribute the medication to the participant.

6.1.3 Dosage, Administration, Schedule

Dose and schedule: We are using the same dose of the oral medication for vapers as we would for cigarette smokers. The participants will be given a dose titrated to 2mg daily which aligns with the current FDA approved dose for smoking cessation. The varenicline prescription will follow the standard induction period: varenicline 0.5 mg once per day for Days 1-3, varenicline 0.5 mg twice per day for Days 4-7, then varenicline 1 mg twice per day (when varenicline reaches peak efficacy for tobacco cessation). Participants will remain on varenicline for 8 weeks total. Dose adjustments (e.g., reduction to 0.5 mg twice per day if 1 mg is not well tolerated) will be allowed at the discretion of the clinical pharmacist/APRN/physician. The entire 8-week supply of varenicline will be shipped at week 1 according to the Pharmacy's workflow..

Medication Schedule: Both groups will follow the same medication schedule (listed below).

- Days 1-3: 0.5mg (or matching placebo) study pill once per day
- Days 4-7: 0.5mg (or matching placebo) study pill twice per day
- Weeks 2-8: 1mg or matching placebo) study pill twice per day

Adverse Events: Other contraindications for varenicline include suicidal ideation.²¹ Suicidality will be assessed at prior to randomization and during the follow-up assessments. If an individual endorses suicidality during the pre-randomization screening, they will be marked as ineligible for the study. This will be assessed using the PHQ9 toolkit for suicide ideation (refer to assessments section). An alert is programmed into the REDCap system that if an individual indicates an active plan to either physically harm or kill themselves, an alert will be sent to the study team. They will then be contacted by our clinical team to complete a risk assessment over via phone. A member of the clinical team will query the participant for details regarding the suicidal ideation, including a likelihood of harming oneself imminently and a plan for committing suicide. If the participant reports an imminent likelihood of harming him/herself or a plan for committing suicide, the clinical team member will call emergency services and will remain on the phone with the participant until emergency services arrive. In the event that the participant expresses an imminent likelihood of harming him/herself, and the connection is lost, emergency services will be contacted to provide emergency services with the participant's contact information, including address. If the participant is not in imminent danger, the clinical staff will provide referrals for local mental health resources and/or instruction to go to the ED or call 911 should suicidal ideation worsen. The clinical

team member will suggest that the participant seek treatment and then will follow-up with the participant via phone one week later.

In the event that a participant endorses suicidal ideation but is not responsive to clinical staff's phone call within 48 hours, the participant will be emailed a list of local mental health resources and will suggest that the participant seek additional treatment. The email will also ask that the participant respond to the clinical staff either via phone or e-mail within 24 hours to confirm receipt of the treatment referrals. Should the participant not respond to the clinical staff's email within an additional 48 hours (4 days from completion of the assessment) and endorse "several days" "More than half the days" or "nearly everyday" to "Thoughts that you would be better off dead or of hurting yourself in some way" on the PHQ9 suicidality toolkit at study screening, emergency services will be contacted and will be provided with the participant's name and address.

We will utilize the PHQ9 assessment to track depression and suicidal ideation during the baseline assessments. If suicidal ideation is endorsed, an automated "red flag" will be processed through our REDCap database. This red flag will indicate either a) a clinically significant increase in total PHQ scoring with an overall score of at least 15 (>5 point increase from baseline and resulting score >15), OR b) any value >0 for item 9/suicidal ideation). The red flag indicators will be monitored daily by our clinical team and will be met with the appropriate measures. These measures are based on prior MUSC-IRB approved protocols of varenicline (i.e., the STARS Pro00098479).

Compliance: The weekly assessments will have questions built in ascertaining information about their medication adherence. We will prompt them through text if the assessments show that they are not compliant.

This study is under review for and Investigational New Drug Application exemption.

6.1.4 Method of Assignment/Randomization

Randomization: 20 participants per site (MUSC and Yale) will be stratified by status of former or never smoker. Former smoker is defined as an individual who has smoked at least 100 cigarettes in their lifetime but have not smoked in the past 6 months or longer.

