5.1 General Design Description

For this preliminary, proof-of-concept study, we require smartphone ownership or email access to allow for receipt of weekly surveys (via text or email) during the sampling period, as well as weekly assessments (methods described below). According to the latest Pew survey, 77% of Americans own a smartphone; >73% among those under age 65. Requirement for smartphone ownership will not affect internal validity, but it could reduce external validity.²

This is a randomized, placebo-controlled, double blind pilot study. This study aims to enroll 20 adults who report daily mono- e-cigarette use at MUSC and 20 adults who report daily mono- e-cigarette use at Yale (N=40 total). This is a 12-week study with 8 weeks of study drug use (either varenicline or placebo) provided to the enrolled participants.

Inclusion/exclusion criteria will be determined via initial online screening and then confirmed with tele-video/phone call final screening. Non-pregnancy verification will be ascertained via remote pregnancy test. If any of these exclusions are endorsed, then the potential participant will not be enrolled into the study. Once screening and informed consent are complete, eligible participants will be randomized to 1 of the following 2 groups:

- 1) VRN + Self-Change Pamphlet
- 2) Placebo + Self-Change Pamphlet

All participants will be asked to provide assessments (as described below) throughout the sampling process to assess vaping & smoking behavior (if the participant initiates smoking after enrolling in the trial), craving, varenicline/placebo use, use of web-based program, etc.

Randomization: 20 participants per site (MUSC and Yale) will be stratified status of former or never smoker. Former smoker is defined as an individual who has smoked at least 100 cigarettes in their lifetime but have not smoked in the past 6 months or longer.

Study Details

Guided Self-Change Booklet: This 3-page pamphlet includes information on how to reduce and quit e-cigarettes on their own (on Page 1), how to prevent relapse to combustible cigarettes (for mono vapers who quit combustible cigarettes by vaping; on Page 2), and how to enroll in the online This is Quitting services (described above; on Page 3).

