6.2 Assessments

6.2.1 Efficacy

Study Assessments

The following tools will be used for the assessments conducted at baseline (week 0) and end of follow-up (Week 0, 8 & 12).

Demographics (Week 0): This questionnaire will collect basic demographic information for each subject including gender, ethnicity/race, employment status, etc.

Smoking/Tobacco Use History (Week 0): This will collect basic info about smoking and smoking cessation history, prior varenicline use, e-cigarette history, tobacco and nicotine product flavor preference, etc.

Modified Questionnaire on Smoking Urges (QSU) (Week 0, 8 & 12): This 3-item assessment is used to examine smoking related urges such as desire to smoke, anticipation of immediate positive outcome, etc.³¹E-cigarette Dependence (Week 0 & 8): The NIH Patient-Reported Outcomes Measurement Information System (PROMIS) measure for daily smokers has also been adapted to measure for use of other tobacco products.^{30, 40} This is a 4-item e-cigarette dependence questionnaire that measures withdrawal and craving.

E-cigarette Dependence Index (Week 0 & 8): This is a 10-item e-cigarette dependence questionnaire that measures difficulty quitting, withdrawal and cravings.⁵⁷

Subjective Effects Cigarettes and E-cigarettes (Week 0, Week 4): Participants will report on subjective evaluation about cigarettes and e-cigarettes. Subjective evaluation includes items derived from the Modified E-Cigarette Evaluation Questionnaire (meCEQ)⁵⁸ that have also been adapted for alternate tobacco products. It measures the degree to which participants experience reinforcing effects from smoking and e-cigarettes. The scale yields five clusters or domains: Smoking Satisfaction, Psychological Reward, Aversion, Enjoyment of Respiratory Tract Sensations, and Craving Reduction.⁵⁶

Patient Health Questionnaire-9 (PHQ9) (Week 0 and Bi-Weekly): which assesses for depression and includes an item on suicidal ideation.⁵⁰

Wisconsin Withdrawal Scale Brief (WSWS2-B): This 6-item scale assesses current symptoms of nicotine withdrawal including cravings and irritability.⁵⁹

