6.3 Study Procedures

This study aims to enroll 20 adults who report daily mono- e-cigarette use at MUSC and 20 adults who report daily mono- e-cigarette use at Yale (N=40 total). This is a 12-week study with 8 weeks of study drug use (either varenicline or placebo) provided to the enrolled participants. Inclusion/exclusion criteria will be determined via initial online screening and then confirmed with tele-video/phone call final screening. Non-pregnancy verification will be ascertained via remote pregnancy test. If any of these exclusions are endorsed, then the potential participant will not be enrolled into the study. Once screening and informed consent are complete, eligible participants will be randomized to 1 of the following 2 groups:

- 1) VRN + Self-Change Pamphlet

2) Placebo + Self-Change Pamphlet

All participants will be asked to provide assessments (as described below) throughout the sampling process to assess vaping & smoking behavior (if the participant initiates smoking after enrolling in the trial), craving, varenicline/placebo use, use of web-based program, etc.

Randomization: 20 participants per site (MUSC and Yale) will be stratified by status of former or never smoker. Former smoker is defined as an individual who has smoked at least 100 cigarettes in their lifetime but have not smoked in the past 6 months or longer.

Study Details

Guided Self-Change Booklet: This 3-page pamphlet includes information on how to reduce and quit e-cigarettes on their own (on Page 1), how to prevent relapse to combustible cigarettes (for mono vapers who quit combustible cigarettes by vaping; on Page 2), and how to enroll in the online This is Quitting services (described above; on Page 3).

All groups will receive this pamphlet as a brief behavioral component of the intervention. This 2-page pamphlet will include information on how to reduce and quit e-cigarettes on their own on one page, how to prevent relapse to combustible cigarettes (for mono vapers who quit combustible cigarettes by vaping) on the second page, and the third page will contain information about how to enroll in the Truth Initiative/Mayo "This is Quitting" online self-guided e-cigarette treatment program (described below).

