6.4 Statistical Method

6.4.1 Statistical Design

Baseline demographic and clinical characteristics will be tabulated for the overall study cohort as well as stratified by randomized treatment assignment. Baseline characteristics will be assessed for association with the primary study abstinence outcomes using univariable logistic regression models and resulting effect sizes will be reported. The primary purpose to this pilot trial is to ascertain study efficacy and determine effect sizes of varenicline on vaping abstinence. End of treatment and study follow up 7-day point prevalence abstinence rates will be tabulated and compared between varenicline, and placebo treated participants using a modified Poisson regression approach. Proportion abstinent as well as risk ratios and associated 95% confidence intervals will be provided for the entire study time course as well as stratified by study time point (end of treatment, study follow-up). Initial models will be adjusted for baseline vaping behavior as well as strata utilized in the randomization procedure. Sensitivity analysis will be employed to compare results from available study data to those with missing study data imputed to vaping (single imputation to worst case outcome). Study results will be utilized to design and sufficiently power a follow up RCT.

Secondary analysis of average reported vaping puffs per day and vaping days per week will be examined using generalized linear mixed effects models (GLMMs). Vaping puffs will be summarized weekly and differences between randomized treatment groups will be assessed during the treatment and follow up time periods. Model based means and standard errors will be used to determine pairwise comparisons and meaningful time points (weeks 8 and

12). The number vaping days per week will be assessed using GLMMs with a negative binomial specified distribution for count data. Median (inner quartile range) vaping days as well as risk ratios and associated 95% confidence intervals will be provided. Longitudinal models will include study treatment, week, and the associated interaction when appropriate.

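### Do the former/never-smoker strata leave recent quitters without a stratum, and would that affect the trial?

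*Combined protocol and SAP*

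**What the plan says.** Sections 5.1, 6.1.4 and 6.3 give the same scheme: "20 participants per site (MUSC and Yale) will be stratified by status of former or never smoker". A former smoker is a person who has "smoked at least 100 cigarettes in their lifetime but have not smoked in the past 6 months or longer". The never-smoker level is not defined, and there is no third level or default rule.

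Section 5.3.2 sets a shorter look-back. Inclusion 7 bars combustible tobacco for the past 30 days. Inclusion 7a adds: "In the 2 months prior to the past 30 days, patients must not use combustible tobacco for >1 time per week". Nothing limits smoking before that. Inclusion 3 requires "use of an e-cigarette containing nicotine > 6 months".

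The stratum reappears in the analysis. Section 6.4.1 states: "Initial models will be adjusted for baseline vaping behavior as well as strata utilized in the randomization procedure". Section 6.2.1 includes a week-0 smoking and tobacco history: "This will collect basic info about smoking and smoking cessation history, prior varenicline use".

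**The concern.** A stratification factor should place every eligible person in exactly one level. Here the former-smoker level needs six months without smoking, while eligibility looks back about three. Someone with 100 or more lifetime cigarettes who quit, say, four months ago is eligible, is not a former smoker as defined, and is not a never smoker in the ordinary sense of the term.

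Staff at two sites would have to choose a level for such a person, and might choose differently. That label would then guide treatment assignment and enter the abstinence models as a covariate. At stake would be arm balance on smoking history and a stratum variable with the same meaning at both sites, in a pilot whose results are meant to design a larger trial.

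**Working it through.** **1. The window.** Take a person with 100 or more lifetime cigarettes and count days since the last one.

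- Eligibility look-back (inclusions 7 and 7a): 30 + about 61 = 91 days.
- Former smoker: six months, about 183 days.
- Eligible but not former: days 31 to 182, which is 182 − 30 = 152 days. Taking six months as 180 to 184 days gives 149 to 153.
- On days 31 to 91, only people who smoked at most once a week qualify (61 / 7 = 8.7, so about 8 or 9 occasions). On days 92 to 182 (91 days), any earlier frequency is allowed.

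Inclusion 3 narrows this to people who still smoked at some point while already vaping. It does not close the gap.

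One qualification: because never smoker is undefined, nobody fails that level by its written terms. Read as everyone who is not former, it makes the strata exhaustive, though oddly labelled.

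**2. Would anyone fall in it?** The documents give no share, s. The chance of at least one among 40 is 1 − (1 − s)^40: 33% at s = 1%, 55% at 2%, 87% at 5%. Shares of 5, 10 and 20% mean 2, 4 and 8 people.

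**3. Balance, by simulation.** Assumptions not in the documents: blocks of 4 within site by stratum; 20 per site; half of participants ever-smokers, including the gap group; placebo abstinence 35, 25 and 15% for never, former and gap; a treatment effect of +20 points. Four rules were compared: ever/never at 100 cigarettes; all gap people to never; a coin flip; one site to former and the other to never.

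Mean absolute arm difference, in people, among all **ever-smokers** (8,000 runs per cell):

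| Gap share | Ever/never | All to never | Coin flip | By site |
|---|---|---|---|---|
| 5% | 0.99 | 1.46 | 1.26 | 1.24 |
| 10% | 1.00 | 1.80 | 1.45 | 1.44 |
| 20% | 1.00 | 2.12 | 1.76 | 1.67 |

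The chance of a difference of 4 or more is 0.3% for ever/never at a 10% share, against 12.4, 5.7 and 5.4%. At 20% it is 0.4% against 19.2, 11.7 and 10.0%.

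This yardstick is the variable that the ever/never rule stratifies on, so that rule wins by construction. The protocol's own factor is the six-month **former smoker** (6,000 runs per cell):

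| Gap share | Ever/never | All to never | Coin flip | By site |
|---|---|---|---|---|
| 5% | 1.35 | 1.00 | 1.19 | 1.18 |
| 10% | 1.63 | 1.00 | 1.37 | 1.36 |
| 20% | 1.86 | 0.99 | 1.53 | 1.47 |

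The chance of 4 or more is now 8.8% for ever/never at 10%, against 0.4, 4.4 and 4.2%. At 20% it is 13.7% against 0.3, 7.4 and 6.0%. The ordering reverses. For the gap people alone, at a 20% share, the mean difference is 1.74 under ever/never against 1.82 to 2.02, so no rule balances them well.

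**4. The treatment estimate.** Across all rules and shares the mean risk difference was 0.197 to 0.202 (true value 0.20), with a standard deviation of 0.148 to 0.153. The label is fixed before assignment and assignment is random within it, so an odd or inconsistent label cannot favour an arm.

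**The case for a change.** The best case for a change is that these people are foreseen. Inclusion 7a expressly tolerates occasional smoking in the second and third months before entry, and section 2.2 itself describes continued smoking as common among e-cigarette users. Even a 1% share gives a one-in-three chance of a case. Reading never smoker as everyone else would label someone who smoked six weeks ago a never smoker, and under that reading balance among ever-smokers is poorest. A clarifying sentence in three sections and one database field would cost little.

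Much of this stands: the gap, the awkward label and the chance that a case arises. The claim of harm does not. The loss of balance appears only if ever-smoking is taken as the history that matters; on the threshold the protocol states three times, the ever/never repair does worse than every ad hoc rule tested. Choosing between them is a trade-off that the documents do not settle.

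The higher shares are also demanding for a trial that recruits exclusive vapers: 20% of participants with half ever-smokers means 20 / 50 = 40% of all ever-smokers smoked within the past six months. Smoking history is reviewed before randomisation (sections 5.1 and 6.3) and recorded at week 0, so a uniform variable may be recoverable for reporting. That last point is only partial comfort, since section 6.2.1 promises basic information and does not name the date of the last cigarette.

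**Conclusion.** The definitions leave a window of about 152 days in which an eligible ever-smoker has no clearly assigned stratum. This is a gap in wording that staff must fill before they can randomise, and it does not alter what the trial would conclude. Bias is ruled out by the order of events. The simulated loss of precision is negligible: the standard deviation is about 0.15 under every rule. The gain in balance from redefining the strata depends on which smoking history one chooses to balance, and it reverses on the protocol's own factor. No change to the plan is called for.

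The size of the window and the absence of bias rest on the documents and the design. The balance and precision figures rest on the assumed block size, site-by-smoking strata, smoker shares and abstinence rates. The number of people affected is unknown.
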